### **3. Data Collection and Management**

#### **3.1. Source Documents**

Source data is all information, original records of clinical findings, observations, or other activities in a clinical trial necessary for the reconstruction and evaluation of the trial. Source data are contained in source documents. Examples of these original documents, and data records include: hospital records, clinical and office charts, laboratory notes, memoranda, subjects' diaries or evaluation checklists, recorded data from automated instruments, copies or transcriptions certified after verification as being accurate and complete, subject files, and records kept at the food dispensing company, and at the laboratories.

#### **3.2. Case Report Forms**

The study case report form (CRF) is the primary data collection instrument for the study. All data requested on the CRF must be recorded. All missing data must be explained.

Data on CRFs will be collected via direct electronic data capture using a secure web-based database designed by and housed in the University of North Carolina. The eCRFs will be the source document in some cases. These eCRFs will not include PHI or participants' identifiable information. Instead, eCRFs will be labeled with a unique study identification number.

Study personnel are instructed that if a space on the CRF is left blank because the procedure was not done or the question was not asked, type "N/D". If the item is not applicable to the individual case, type "N/A".

#### **3.3. Data access**

##### **TO BE COMPLETED WITH HELP FROM UNC**

During the conduct of the trial, the data management team at the University of North Carolina and the lead data analyst at the University of Pennsylvania will have access to the raw study data. Standardized reports will be generated to allow data coordinating center to monitor recruitment and retention, completion of eCRFs, and for quality control purposes prior to the end of the trial. The analyst will prepare summary documents for the investigative team without separating the data by study group. The analyst will prepare separate files stratifying the data by study group for the data and safety monitoring board (DSMB).

At the conclusion of the trial, the data analyst and study biostatistician will prepare the analytic data files to be used in the final analyses. They will work with the data coordinating center and the data management team to resolve any outstanding queries prior to conducting the final analyses. Review of descriptive data of the combined cohort may be conducted with the data management team and the data coordinating center to facilitate data cleaning.

The analytic plan will be reviewed and agreed upon by the data coordinating center and study steering committee prior to conducting the final analyses. A copy of the locked final analytic data set will be preserved as a backup. All analyses will be conducted using fast computer programs such that no changes will be made to the locked final data set.

### **4. Data collection**

Baseline and follow-up data will be collected through a combination of electronic CRFs completed by the participants and by the research team. The former will be used to collect symptoms used to define the PROs. The latter will be used to collect data on patient characteristics and adverse events.

Baseline data are described in the following table.

Variable	Variable name	Categorization
Age		Continuous

Sex		Male=0; Female=1
Race		Caucasian=0; Black=1; Asian=3; American Indian / Alaska Native=4; Pacific Islander / Hawaiian = 5; Multi racial = 6
Ethnicity		Non-Hispanic=0; Hispanic=1
Weight in Kg		Continuous
BMI		Continuous
Tobacco use		0=never; 1=former; 2=current
Current medications		
Current corticosteroid use		0=no; 1=yes
Current mesalamine use		0=no; 1=yes
Current azathioprine or 6MP use		0=no; 1=yes
Current methotrexate use		0=no; 1=yes
Current anti-TNF use		0=no; 1=yes
Current vedolizumab/natalizumab		0=no; 1=yes
Former medications		
Former corticosteroid use		0=no; 1=yes
Former mesalamine use		0=no; 1=yes
Former azathioprine or 6MP use		0=no; 1=yes
Former methotrexate use		0=no; 1=yes
Former anti-TNF use		0=no; 1=yes
Former vedolizumab or natalizumab		0=no; 1=yes
Disease distribution		
Ileum		0=no; 1=yes
Colon		0=no; 1=yes
Ileocolon		0=no; 1=yes
Duration of current flare		Continuous in days
Current symptoms		
Bowel frequency		Continuous
Abdominal pain rating		Ordinal
General Wellbeing		Ordinal
Fatigue (PROMIS)		Continuous
Sleep (PROMIS)		Continuous
Pain interference (PROMIS)		Continuous
Social Isolation (PROMIS)		Continuous
Baseline diet from DHQ		
Percent calories from Fat		Continuous
Percent calories from Carbohydrates		Continuous
Percent calories from Protein		Continuous
Gluten free diet		0=no; 1=yes
Other dietary descriptions – [name]		
Back pain screening*		
Age at onset <40 years		0=no; 1=yes
Insidious onset		1=no; 0=yes
Improvement with exercise		0=no; 1=yes
Improvement with rest		1=no; 0=yes
Wake up in the second half of the		0=no; 1=yes

night with pain		
Bath Index if screen positive for back pain		Continuous

\*If at least four out of these five parameters were fulfilled, the criteria had a sensitivity of 77.0% and specificity of 91.7% for axial spondyloarthritis in the patients participating in the workshop, and 79.6% and 72.4%, respectively, in the validation cohort.

Baseline and follow-up clinical data will be collected as described in the following table

Variable	Variable name	Categorization	Data source	When collected
Number of liquid or soft stools each day		Continuous	Participant	Daily
Abdominal pain		0=none; 1=mild; 2-moderate; 3=severe	Participant	Daily
General wellbeing		0=generally well; 1=slightly under par, 2=poor; 3= very poor; 4= terrible	Participant	Daily
Arthralgia		0=no; 1=yes	Investigator	0,6,12
Uveitis		0=no; 1=yes	Investigator	0,6,12
Erythema nodosum		0=no; 1=yes	Investigator	0,6,12
Abscess		0=no; 1=yes	Investigator	0,6,12
Pyoderma gangrenosum		0=no; 1=yes	Investigator	0,6,12
Fissure		0=no; 1=yes	Investigator	0,6,12
New fistula		0=no; 1=yes	Investigator	0,6,12
Abscess		0=no; 1=yes	Investigator	0,6,12
Aphthous ulcers		0=no; 1=yes	Investigator	0,6,12
PROMIS measures				
Pain Interference 6a short form		Continuous	Participant	0,6,12
v1.0 Fatigue 7a short form		Continuous	Participant	0,6,12
v1.0 Sleep Disturbance 8a short form		Continuous	Participant	0,6,12
V2.0 Social Isolation 4a				
RAPID-3		Continuous	Participant	0,6,12
BASFI*		Continuous	Participant	0,6,12

\* Only if screen positive on back pain screen

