#### **5.5.1.6. Physical function and joint pain**

Physical function and joint pain will be assessed with a subset of core variables found in the Multi-dimensional Health Assessment Questionnaire (MD-HAQ). We will screen for inflammatory back pain using the criteria developed by Sieper et al. and assess symptom severity with the Bath AS Functional Index in those who screen positive.

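### SAP section 4 codes insidious onset as 1=no; 0=yes; if the printed codes are counted for the 4-of-5 back-pain rule, the Bath index goes to a partly wrong subset

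*Combined protocol and SAP*

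**What the plan says.** The baseline table in SAP section 4 has a block of five back-pain screening items, each with a numeric code. Three are coded forward: onset before 40 ("Age at onset <40 years 0=no; 1=yes"), relief with exercise ("Improvement with exercise 0=no; 1=yes") and waking with pain in the second half of the night (also 0=no; 1=yes). Two are reversed: "Improvement with rest 1=no; 0=yes" and "Insidious onset 1=no; 0=yes".

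The footnote to the block supplies the only counting rule, as part of a statement of published accuracy: "If at least four out of these five parameters were fulfilled, the criteria had a sensitivity of 77.0% and specificity of 91.7" per cent in the workshop patients, and 79.6% and 72.4% in the validation cohort.

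The screen controls data collection. The follow-up table in the same section lists the Bath index (BASFI) at weeks 0, 6 and 12 with the restriction "Only if screen positive on back pain screen". SAP section 5.5.1.6 says the trial will "assess symptom severity with the Bath AS Functional Index in those who screen positive". SAP section 5.5.3 compares the index between arms as a continuous measure. It belongs to the joint-symptom part of secondary objective 3 (protocol section 2.3).

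**The concern.** Exercise and rest are mirror-image items, and the table codes them in opposite directions. The natural explanation is that 1 marks the answer that fulfils the parameter: relief with exercise, and no relief with rest. On that reading the point for insidious onset should go to participants who have it. The printed code gives it to those who do not. The name of the rest item has to be negated for its code to make sense; nothing in the documents gives a reason to negate insidious onset.

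The two SAP section 4 tables contain 30 yes/no rows. All but these two are coded 0=no; 1=yes, and both exceptions sit in the one block that carries a counting rule. The insidious-onset code looks like a reversal carried over from the rest row.

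At stake is who is measured. Item answers can be re-scored later, but a Bath index that was never administered cannot be recovered.

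**Working it through.** **Inputs.** The five codes and the threshold of four are from the SAP section 4 baseline table and footnote. The restriction of the Bath index to screen positives is from the follow-up table and section 5.5.1.6. The published sensitivity and specificity cannot be reproduced, because the documents give no item-level data.

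**Set-up.** Let each feature be 1 when it points towards a positive screen: onset before 40, insidious onset (call it *i*), relief with exercise, no relief with rest, night waking. The intended count is T, the sum of the five. The printed table reverses only *i*, so the printed count is

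R = T − i + (1 − i) = T + 1 − 2i.

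Hence R = T − 1 when onset is insidious and R = T + 1 when it is not. A positive screen is a count of at least 4.

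**Enumeration of all 2^5 = 32 patterns.**

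| Insidious onset | Other features present | Patterns | T | R | Intended | As printed |
|---|---|---|---|---|---|---|
| yes | 4 of 4 | 1 | 5 | 4 | positive | positive |
| no | 4 of 4 | 1 | 4 | 5 | positive | positive |
| yes | 3 of 4 | 4 | 4 | 3 | positive | **negative** |
| no | 3 of 4 | 4 | 3 | 4 | negative | **positive** |
| either | 2 or fewer | 22 | ≤3 | ≤3 | negative | negative |

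Both codings give six positive patterns, but only two are shared. Four are wrongly rejected and four wrongly admitted: 4 + 4 = 8 of 32.

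**From patterns to participants (illustration only).** Assume five independent items, each present with probability p.

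- Intended positives: 5p⁴(1−p) + p⁵
- Wrongly rejected: 4p⁴(1−p)
- Wrongly admitted: 4p³(1−p)²
- Positives as printed: p⁵ + p⁴(1−p) + 4p³(1−p)²

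At p = 0.8, intended positives are 0.4096 + 0.3277 = 0.7373, and 0.3277 / 0.7373 = 44.4% of them are rejected. Positives as printed are 0.3277 + 0.0819 + 0.0819 = 0.4915, and 0.0819 / 0.4915 = 16.7% of them are false. At p = 0.6 the two shares are 61.5% and 51.6%; at p = 0.5 both are 66.7%.

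**Effect on the published accuracy (same independence assumption).** With equal item frequencies chosen to give the stated sensitivity, the printed coding lowers it from 77.0% to about 52% (workshop) and from 79.6% to about 54% (validation). If instead insidious onset is present in 50% to 95% of cases, workshop sensitivity under the printed coding runs from 77% down to 40%, and validation sensitivity from 80% down to 43%. At 30% presence it would rise to about 88% and 89%. With equal item frequencies, specificity goes from 91.7% to about 88.6% and from 72.4% to about 76.3%, so it can move either way.

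**The case against.** The strongest reply is that the harm has not been shown to occur. No section says the codes are added; the footnote speaks of parameters being fulfilled and reports accuracy. The criteria are in Appendix J (protocol sections 3.4.2.2 and 16), which is not in the available text, and no section describes logic that triggers the Bath index. The table also looks unfinished: the variable-name column is blank, the race codes skip 2, and the section before it (3.3) is marked as still to be completed. A slip here is weak evidence that the form is wrong. That stands, and it makes the consequence conditional. It does not clear the table: if the codes are only labels, two unexplained reversals remain beside a rule that never says which answer fulfils each item.

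The direction of the insidious-onset criterion is also not stated in words. It is inferred from the item's name and from the exercise/rest pairing. That stands too, and is why Appendix J should be checked.

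A reader might infer that the screen turns away typical inflammatory back pain and measures the wrong group altogether. The enumeration does not support this: all five features score 4 and pass, and two of the six intended positive patterns survive. Nor are the 44–67% missed and 17–67% false shares estimates for this trial. They assume independent, equally frequent items. Features of one condition may cluster, which would put more participants at five of five, where they still pass, and the missed share could fall below 44%.

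Finally, the consequence is small. Protocol section 2 calls the secondary aims exploratory, the Bath index is collected only in a subset, and RAPID-3 carries no such restriction. That is correct and limits the weight of the point.

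**Conclusion.** The row is wrong as written, on the reading that the block itself suggests. If the printed codes are counted for the 4-of-5 rule, 8 of 32 patterns are misclassified: participants with insidious onset and exactly three of the other four features are screened out, and those without it and with exactly three others are admitted. The Bath index would then be collected in a partly wrong subset, and the quoted accuracy would not describe the screen in use.

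This rests on two assumptions: that 1 is meant to mean fulfilled, and that the form or the analysis uses the printed codes. The documents support the first by inference and are silent on the second. They give no basis for a percentage of participants affected.

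A reader might also suspect bias between the diets. The screen is listed as baseline data, and joint symptoms are collected at Visit 1, before randomization, so the error does not by itself favour either arm. It changes who is in the subset. The primary endpoint, sample size, power and alpha are unaffected.

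**What to change.** In the SAP section 4 baseline table, change insidious onset to 0=no; 1=yes, after confirming against the Appendix J criteria that insidious onset is the fulfilling answer. Keep improvement with rest at 1=no; 0=yes. Add one sentence saying that 1 means the parameter is fulfilled and that a sum of 4 or more is a positive screen. Check that any data-system logic releasing the Bath index uses this coding, and re-score anyone already screened from their item answers.

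The cost is one table row, one sentence and one logic check. It is best done early, since re-scoring cannot supply Bath values that were not collected.

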#### **4.1. Best Practices in Administration of PROMIS measures**

- PROMIS self-report measures are intended to be completed by the respondent without help from anyone else.
- If respondents are unable to answer on their own, have someone else (“proxy”) report on their behalf. Respondents requiring a proxy may include: young children, people in the early stages of dementia who may not recognize the extent of their impairment, people with cognitive or communication deficits, and people with severe disease burden. PROMIS Parent Proxy measures are available.
- Keep respondents’ privacy in mind, but have staff readily available to help with any technology issues that may arise.
- It is acceptable for staff to define a term (e.g., “nausea”), but not to define a concept where the respondent’s subjective interpretation is the goal of the question (e.g., “quality of life”).
- Utilize the same method (e.g., computer, telephone, or paper) and mode (e.g., self vs. interviewer) of administration. However, this is not always possible, and PROMIS measures have produced similar scores when the method of administration varied. See the Forum for more information on **method / mode** effects.
- In clinical settings, give respondents the optimal time needed to capture the most relevant perspective and complete data (e.g., before/after clinician visit or in between visits). This may depend on the study aims and/or clinic work flow.
- The text and responses of PROMIS items cannot be altered in any way and still be considered a PROMIS item. Users are welcome to modify the items, but cannot refer to these modified items as PROMIS and we have no data about whether or not this modified version would have the same psychometric properties as the original PROMIS item. If you do modify items, please clearly specify in what ways the items were modified in any publications or other publicly disseminated work products.

There are multiple different versions of the PROMIS measures. The recommended shortform versions can be found at <http://www.healthmeasures.net/applications-of-healthmeasures/in-research/selecting-a-healthmeasure>. For pain interference, v1.0 Pain Interference 6a short form is recommended. For fatigue, v1.0 Fatigue 7a short form is recommended. For sleep, v1.0 Sleep Disturbance 8a short form is recommended. For social isolation, we selected a brief version (Social Isolation Short Form 4a). Scoring guidelines are included in the appendices. We will use the PROMIS Assessment Center Scoring Service to obtain the most accurate scores.

### **5. Analytic plan**

#### **5.1. Overview**

[figure not shown]
This clinical trial will examine the effects of a low risk intervention. A total of 194 participants are anticipated to be included in the study. Enrollment is anticipated to be completed over a two-year time period. Because this clinical trial will compare two different diets, both of which have potential health benefits, no interim safety or effectiveness analyses are planned. However, analyses will be conducted to monitor recruitment, retention, and data quality.

## 5.2. Sample size

The study is designed to enroll 97 patients into each of the treatment arms. Specific aims 1 and 2 will be considered separately and no reduction in type 1 error will be applied for multiple testing. The anticipated remission rate in the group receiving the MSD is unlikely to exceed 40% given the historical remission rates in placebo arms of Crohn's disease trials and assuming only a modest therapeutic benefit of this less restrictive of the two diets. Sample size calculations assume no loss to follow-up since all participants who are lost to follow-up will be categorized as non-responders in the analyses of both dichotomous primary outcomes (symptomatic remission and reduction in mucosal inflammation). Our PPRN Patient Governance Council met and determined that the minimum clinically important difference in remission rates is 20% as smaller differences are unlikely to justify the challenges of following a strict restriction diet such as the SCD. Thus, we used an anticipated remission rate of 40% with the MSD and 60% with the SCD to determine the sample size. With 97 participants per group, the study will have 80% power with a type 1 error of 5% to detect a difference of 40% vs 60% in effectiveness of the two diets using a chi test.

In reality, we anticipate that the remission rate in the MSD will be less than 40%. The power curve shown below depicts the power to detect a 20% difference based on the remission rate in the MSD arm of the trial where  $p_1$  represents the remission rate in the SCD arm (i.e.,  $p_1=0.3$  represents power to detect a difference of 10% vs 30% across a sample size ranging from 60 to 120). With 97 participants per group, there is more than 90% power to detect a difference of 10% vs 30% and 80% power to detect a difference of 40% vs 60%.

Finally, all of the power estimates are likely slight under estimates. We expect even more power when the Cochran-Mantel-Haenszel (CMH) chi test is used since we expect that the odds ratios in different strata are in the same direction.

Viewed alternatively, with 97 participants per arm, there is 80% and 90% power to detect the following differences based on the effectiveness of the control diet (i.e. the MSD).

Proportion of MSD group achieving the outcome	80% power to detect an absolute difference (SCD - MSD) greater than or equal to	90% power to detect an absolute difference (SCD - MSD) greater than or equal to
10%	15%	18%
20%	18%	21%
30%	20%	22%
40%	20%	23%

Assumes 97 participants per group, type 1 error rate of 5%, and chi test

All power calculations were computed using PS Power and Sample Size Calculations Version 3.0, January 2009 (Copyright © 1997-2009 by William D. Dupont and Walton D. Plummer).

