### 2. Overview

This is a randomized, multicenter, comparative effectiveness trial of the specific carbohydrate diet (SCD) and a Mediterranean style diet (MSD) to induce remission in patients with Crohn's disease. The study is funded by PCORI, will be conducted in up to 50 centers throughout the United States over a period of three years.

The primary and secondary objectives of this clinical trial are the following:

*Primary:*

1. To compare the effectiveness of the specific carbohydrate diet and a Mediterranean style diet to induce symptomatic and clinical remission in patients with Crohn's disease.
- 2.
3. *Secondary:*
  1. To compare the effectiveness of the specific carbohydrate diet and a Mediterranean style diet to reduce mucosal inflammation in patients with active Crohn's disease. Mucosal inflammation will be assessed by measuring the concentration of calprotectin in the feces (FCP).
  2. To compare the effectiveness of the Specific Carbohydrate Diet and a Mediterranean style diet to reduce systemic inflammation in patients with active Crohn's disease. Systemic inflammation will be assessed by measuring the concentration of C reactive protein (CRP).
  3. To compare the effectiveness of the specific carbohydrate diet and a Mediterranean style diet to improve the following symptoms in patients with Crohn's disease: a) fatigue, b) pain, c) joint symptoms.
  4. To determine the proportion of patients who continue the study diets when prepared food is no longer provided without cost and the reasons for discontinuation of the diets.

The clinical trial will enroll 194 participants who will be randomly assigned in a 1 to 1 ratio to the two study diets. The main inclusion criteria are Crohn's disease with mild to moderately active symptoms as measured by the short CDAI (sCDAI) score greater than 175 and less than 400, and at least 18 years of age. The main exclusion criteria are the following:

- Pregnancy
- Hospitalized pts. or surgery planned within 6 wks
- Ostomy or known symptomatic intestinal stricture
- Start of thiopurines, natalizumab, vedolizumab or methotrexate (w/in 12 wks) or anti-TNF (w/in 8 wks)
- Start or change corticosteroids within 1 week of screening or dose >20mg prednisone or equivalent
- Use of antibiotics w/in 2 weeks of screening
- Start or change of dose of 5-ASA type medication w/in 2 weeks of screening
- Baseline stool frequency >4 bowel movements/day when well
- BMI<16 or ≥40

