### **5.5. Efficacy Analysis**

Analysis of the primary outcome: The primary outcomes will be measured at 6 weeks after the start of the study diets. The primary analyses for the RCT will use 2-sided tests of statistical significance and will be performed using the intention-to-treat principle. Thus, patients will be classified according to the study arm that they were assigned, regardless of the amount of food from the assigned diet consumed.

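### SAP 5.2 has one wrong cell in the detectable-difference table (MSD 30%, 90% power: 22 points printed, 23 needed) and an unsupported claim of extra power from the CMH test; the sample size itself is correct

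*Combined protocol and SAP*

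**What the plan says.** SAP section 5.2 (Appendix G) sizes the trial on remission of 40% with the MSD and 60% with the Specific Carbohydrate Diet (SCD), 80% power and a 5% type 1 error, using a chi-square test: "The study is designed to enroll 97 patients into each of the treatment arms". It adds that power exceeds 90% for 10% versus 30%, and that MSD remission is expected to be below 40%.

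A table follows, introduced by the statement that "there is 80% and 90% power to detect the following differences based on the effectiveness of the control diet". For MSD remission of 10, 20, 30 and 40% it prints differences of 15, 18, 20 and 20 points at 80% power, and 18, 21, 22 and 23 points at 90% power. Its footnote reads "Assumes 97 participants per group, type 1 error rate of 5"%, with a chi-square test.

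Between the power statement and the table, the section says that "all of the power estimates are likely slight under estimates". It expects more power from the CMH test "since we expect that the odds ratios in different strata are in the same direction".

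**The concern.** Two statements in the section do not match its own basis.

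- **The table.** The 90% entry for MSD 30% is only one point below the entry for MSD 40%, and only two points above the 80% entry in its own row. In the other three rows the 80% and 90% entries are three points apart. That suggests a slip in one cell.
- **The CMH remark.** Effects in the same direction keep a stratified test from losing power through cancellation. They do not make it more powerful than the unstratified test. A gain requires the stratum to explain part of the variation in remission.

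What is at stake is the accuracy of the stated power. A reader who takes the 30% row at face value would credit the trial with 90% power where it has about 88%. A reader who accepts the remark would treat every figure in the section as conservative for a reason that does not make it so.

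**Working it through.** **Inputs.** 97 per arm, 5% type 1 error and a chi-square test (SAP 5.2 and the table footnote); two-sided testing, since "The primary analyses for the RCT will use 2-sided tests of statistical significance" (SAP 5.5); equal arms, "randomly assigned in a 1 to 1 ratio to the two study diets" (SAP section 2). There is no allowance for dropout, because losses count as non-responders (SAP 5.2).

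**Formula.** For rates p1 and p2, with mean rate m = (p1 + p2)/2 and n per arm:

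power = Φ{ [ |p2 − p1| − 1.96·√(2m(1−m)/n) ] / √( [p1(1−p1) + p2(1−p2)]/n ) }

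**Step 1: reproduce the design figure.** For 40% versus 60%, m = 0.50. The null standard error is √(2×0.25/97) = 0.0718 and the alternative one is √(0.48/97) = 0.0703. Then (0.20 − 1.96×0.0718)/0.0703 = 0.843, and Φ(0.843) = 80.0%. Solving for n at 80% power gives 96.9, so 97. For 10% versus 30% the power is 94.2%. Both statements in the SAP hold.

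**Step 2: the table.** Solving the same formula for the difference at n = 97:

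| MSD rate | 80% power: printed / computed | 90% power: printed / computed |
|---|---|---|
| 10% | 15 / 15.2 | 18 / 18.1 |
| 20% | 18 / 18.2 | 21 / 21.2 |
| 30% | 20 / 19.6 | **22 / 22.7** |
| 40% | 20 / 20.0 | 23 / 23.0 |

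Rounded to whole points, only the cell in bold disagrees.

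**Step 3: power at the printed entry.** For 30% versus 52%, m = 0.41, and the standard errors are 0.0706 and 0.0688. Then (0.22 − 1.96×0.0706)/0.0688 = 1.185, and Φ(1.185) = 88.2%. Exact enumeration of the chi-square test gives 88.1%. At 23 points (30% versus 53%) the formula gives 90.8%. Put as sample size, 90% power needs 103 per arm for 30% versus 52%, and 95 for 30% versus 53%.

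**Step 4: CMH against the unstratified chi-square.** The SAP gives no stratum sizes or rates, so I assumed two nearly equal strata (48 and 49 per arm) and simulated 400,000 trials per scenario. Overall rates were held at about 40% versus 60%. Neither statistic has a continuity correction.

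| MSD to SCD remission, by stratum | CMH | Chi-square |
|---|---|---|
| 40 to 60; 40 to 60 (not prognostic) | 80.7% | 80.7% |
| 40 to 50; 40 to 70 (same direction, unequal effects) | 81.3% | 81.3% |
| 30 to 50; 50 to 70 (strata 20 points apart) | 81.4% | 81.2% |
| 20 to 40; 60 to 80 (strata 40 points apart) | 86.8% | 82.7% |

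The odds ratios point the same way in all four scenarios. A material gain appears only in the last, where the strata differ by 40 points in remission.

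**The case against.** **The cell is only a rounding matter.** The table is in whole points, and other entries also fall a little short of nominal power (79.0% and 89.8% at MSD 10%; 79.4% and 89.4% at MSD 20%). An unpooled variance gives 22.3 for this cell, which rounds to the printed 22, and the SAP does not state the variance form. Part of this stands: the shortfall is small, 1.8 points of power. But those other entries are correctly rounded and this one is not. The unpooled form does not rescue the row either. It gives 19.3 for the 80% cell, where 20 is printed, and still only 89.2% power at 22 points. It would also have given 95 per arm at the design point (94.2 before rounding up), not 97.

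**The CMH conclusion may be true even though its reason is not.** The uncorrected CMH results above all exceed 80%, and the SAP hedges its wording. This stands as far as it goes. In the first two scenarios, however, the unstratified chi-square has the same simulated power, so the small excess over 80.0% is not a gain from stratifying. A real gain is possible if biologic use is strongly prognostic, but the SAP offers nothing to show that.

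**Nothing in the design rests on either point.** This is correct. The sample size was set on 40% versus 60%. For the 20-point difference that the plan calls clinically important, power rises as the MSD rate falls: 81.7% at 30%, 86.6% at 20% and 94.2% at 10%.

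**A stronger reading: the test may fall short of 80%.** A reader might note that a continuity-corrected CMH test would have only 76.5% power at 40% versus 60%. The documents do not support this as a criticism. Protocol section 8.4.2 and SAP section 5.5.2 both equate the CMH test with the score test from conditional logistic regression. That score test carries no continuity correction, so 76.5% describes a test that the plan does not specify.

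**Conclusion.** The point holds as two minor corrections to SAP 5.2.

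- The MSD 30% / 90% power cell should read 23, not 22. The printed difference has 88.2% power (88.1% exact) against a stated 90%. This rests on the table's stated assumptions and on the pooled-variance form that reproduces 97 per arm.
- The claim that all the power figures err low does not follow from odds ratios in the same direction. CMH power at 40% versus 60% is about 80 to 81% unless biologic use is strongly prognostic. The simulated figures depend on the assumed equal strata; the reasoning does not.

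A reader might infer that 97 per arm delivers less than the SAP promises overall. It does not: the design power, the 10% versus 30% statement and the other seven cells all reproduce. Neither point affects the sample size, the primary test or the type 1 error.

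**What to change.** In the detectable-difference table of SAP 5.2, change the MSD 30% / 90% power entry from 22% to 23%.

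Delete the sentences claiming more power from the CMH test, or justify them with assumed remission rates and sizes for biologic users and non-users. In either case, state that CMH power at 40% versus 60% is about 80 to 81% unless biologic use is strongly prognostic for remission.

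The sample size and the primary test stay as they are. The cost is a small SAP text edit and one slightly less favourable figure.
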